Figure 6. Fluoroscopic images of a 5th finger with nodal DIP OA. Panel A was obtained without a finger trap applied. Panel B was obtained with a finger trap applied. The red arrows highlight the increase in the DIP joint space with the finger trap applied.

traps are non-invasive and are not associated with an increased risk for infection. Also, since hands are not a common place for deep venous thrombosis, there is little risk for pulmonary emboli related to their use. Thus, finger traps may provide traction for hand OA without attendant serious adverse events associated with distraction.

We performed fluoroscopy on one volunteer with nodal hand OA, with and without a finger trap applied (Figure 6). With a finger trap there was an increase in the DIP joint space, indicated by the red arrows, as well as in all proximate joints. We also assessed tolerability of the traction orthoses on four volunteers. All were able to wear the orthoses for 30 minutes without any complaints. At 60 minutes, one volunteer complained of numbness that resolved within a few minutes after the finger trap was removed. There were no long-term sequelae related to application of the finger trap orthoses. These preliminary data support that finger trap orthoses provide traction as proposed and can be easily tolerated for a 30 - 60 minute wear time.

**2.8 Expected Aims for the follow-up R01 to this R21.** The findings from this study would provide essential feasibility and preliminary data for a follow up R01 that would fund a larger randomized controlled clinical trial of traction therapy to definitively assess its efficacy as a treatment for hand OA that would impact both structure and symptoms. In this R01, we would deploy comprehensive questionnaire, physical exams, radiographs, and MRIs on all participants for a longer duration of follow up. Information on participant compliance and comfort of the traction orthosis would be used to optimize traction delivery. Effect sizes of traction therapy for hand OA from this R21 would be instrumental in providing appropriate power calculations to design such a study. If we can show efficacy of this therapeutic intervention, this would be an impetus to widely disseminate this therapy for nodal OA.

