## **6.3 Masking and Unmasking.**

Our Statistician, [name], and our research coordinator will only be aware of group designations of A and B. They will be blinded to treatment assignment. Prior to receiving treatment allocation information for the first participant of the study, our OT, [name] will flip a coin to assign whether treatment "A" represent traction orthosis or standard of care. She will keep this designation secret and will not share this designation with study staff or participants. Only our OT will be unblinded to treatment allocation. Opaque storage bags will be provided to the participants to store their orthoses. Our OT will make a specific point to tell the participants that they must store their orthoses in opaque bags when interacting with study staff. Masking will be maintained through the course of the study, during data collection, including when radiographs and MRIs are read and primary analyses are performed. Only when all primary data analyses are completed will our OT reveal which group is treatment "A" and unmask the treatment allocation.

Although we will make every effort to maintain blinding, it may be imperfect, where our research coordinator may accidentally have the treatment allocation revealed to him, by inadvertently seeing the orthosis or the participant might tell him which orthosis he/she received. Should this happen, , this will be viewed as a protocol deviation. Additionally,

we will make notation that our research coordinator may be unblinded to the treatment allocation. In those instances, we will have our alternate research coordinator who is still blinded, administer the treatment outcomes at the subsequent follow up visits.

Should the IRB, KAI, and/or our Safety Officer indicate a need to unblind the study prior to the end of data collection, [name] must confirm the need to unblind the study. Appropriate concerns that could be raised by any of these entities would include if there were unexpected or high numbers of SAEs that occurred in the study. [name] will instruct our OT to reveal which group is treatment "A" to our study statistician, [name], breaking the study blind. All intentional and unintentional blinding will be reported to the IRB, KAI and our Safety Officer.

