### **8.3. Additional co-variates of interest include:**

- age, (Assessed at baseline visit only)
- sex, (Assessed at baseline visit only)
- race / ethnicity, (Assessed at baseline visit only)
- body mass index, (Assessed at baseline visit only)
- co-morbidities, (Assessed at baseline visit only)
- a family history of hand OA, (Assessed at baseline visit only)
- occupations that they have performed in their life, (Assessed at baseline visit only)

- time spent on electronics (including smart phones, tablets, and computers) (Assessed at the baseline, week 4, week 12, and week 24 visits)
- International Physical Activity Questionnaire (iPAQ) questionnaire on physical activity, (Assessed at the baseline, week 4, week 12, and week 24 visits)
- Center for Epidemiologic Studies Depression Scale (CES-D). (Assessed at the baseline, week 4, week 12, and week 24 visits)

These data will help to assess whether randomization was successful and perhaps identify potential mediators to the effect of the traction orthosis.

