We will complete descriptive analyses of baseline characteristics of the treated and control groups to allow assessment of generalizability and success of randomization. We will use either Student t-tests or rank-based nonparametric tests where appropriate. Our primary analytic approach will be to use intention- to-treat (ITT) analyses to compare mean change of each symptom and function outcome during follow-up between traction therapy and the control groups with linear regression model for longitudinal repeated measures data. Missing outcomes among participants who missed pain and function questions or lost to follow up will be addressed by multiple imputation using the Markov chain Monte Carlo method. Under the assumption of missing at random, we will include factors which may be related to missing of outcome in the imputation, such baseline demographic characteristics, disease severity, etc. We can use this method of imputation because all outcomes are continuous and they can be assumed to follow multivariate normality distribution. To use this method of multiple imputations, there is an assumption of missing at random. Though this assumption is not testable, multiple imputation method are viewed as less biased than a completers' analysis, last observation carried forward, and single imputation method.

**Specific aim 4. Imaging outcomes.** Given the exploratory nature of this study, we will be broad in our inclusion of outcome measures we will evaluate. The primary structural outcome measure will be change in sum of the Kellgren and Lawrence score of all DIPs in the hand that was braced. We will also evaluate change in joint space narrowing, and osteophyte scores and the Verbruggen-Veys from baseline to 6 month follow up comparing the traction versus the control groups. For those randomized to traction, we will also compare the hand that received traction to the hand that did not. To address potential missing data, we will use a multiple imputation method, assuming the data are missing at

random. We will perform an ANOVA to compare mean change in the sum of radiographic scores over the 6 month follow up period between the traction therapy and the control groups. If there are unbalanced baseline covariates between the treatment groups, we will use an ANCOVA approach to include them as covariates in the analysis.

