Although hand OA is very common, only a small percentage seek care from their providers for this condition. Therefore, engagement into medical care for hand OA will be useful as a retention strategy. Additionally, participants will all receive durable goods to provide the standard of care for hand OA including a thermal modality and the orthoses made for them by our OT. Also, they will be instructed on range of motion exercises and joint protective strategies that should help their hand symptoms.

Regarding special vulnerable populations, fetuses, neonates, and children will not be eligible for this study because we are targeting veterans who are patients at the MEDVAMC. Pregnant women will be excluded to mitigate any potential risks related to radiation exposure associated with obtaining radiographs and high powered magnetic fields related to obtaining MRIs. We do not expect that prisoners or institutionalized individuals will learn about this study and therefore will not be recruited into the study. Therefore, no vulnerable populations will be included in this study so none of these groups will be placed at increased risk relative to other participants included in our study.

Once a participant is deemed eligible for participation into the study and is consented for the study, he/she will have all his/her baseline assessments administered by the study research coordinator. After this is completed, the research coordinator will email [name], our statistician, who will generate a randomization assignment (designated as group A v. group B) stratified by gender. This allocation assignment will only be transmitted to our OT by email after the OT has also seen the participant at baseline and provided all other non-pharmacologic interventions for hand OA that are considered standard of care. Prior to the beginning of the study, the OT will use a coin flip to decide which group (A v. B) will be the treatment v. control group. The OT will be the only person in the investigative team to know this

designation until the study data set is closed and all analyses are finalized. At that point, the OT will customize the appropriate orthosis for the participant to take with him/her.

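### Aim 4: an undefined imbalance trigger decides whether the primary structure endpoint is analysed by ANOVA or ANCOVA (minor)

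*Combined protocol and SAP*

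**What the plan says.** The primary structure endpoint is the change over 24 weeks in the summed K-L score of the DIP joints of the braced hand (section 3.0, Table 2; section 9.0, Specific aim 4). The default analysis is: "We will perform an ANOVA to compare mean change in the sum of radiographic scores over the 6 month follow up period". The next sentence makes adjustment conditional: "If there are unbalanced baseline covariates between the treatment groups, we will use an ANCOVA approach to include them as covariates in the analysis".

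Three other places bear on how that condition might be read:

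- Under Specific aim 3, beside the description of baseline characteristics, section 9.0 says: "We will use either Student t-tests or rank-based nonparametric tests where appropriate". No significance level is stated.
- Section 8.3 lists ten covariates and says: "These data will help to assess whether randomization was successful". It does not tie them to the Aim 4 ANCOVA, and the baseline K-L sum is not among them.
- Section 6.2 stratifies the permuted-block randomisation by sex. Sex is not named in the Aim 4 model.

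Nothing elsewhere in the document defines imbalance or names the covariates to be used.

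**The concern.** With random allocation, a baseline difference between arms arises by chance. A rule that adjusts only when such a difference appears therefore lets chance choose between two models for a primary endpoint. It also selects covariates on the wrong property. A covariate earns its place by its relation to the outcome, not by how far its arm means happen to differ. The baseline value of the K-L sum, usually the strongest predictor of the follow-up value, gets in only if it happens to be flagged.

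What is at stake is the structure estimate and its standard error. Section 2.8 says of the planned follow-up trial: "Effect sizes of traction therapy for hand OA from this R21 would be instrumental in providing appropriate power calculations to design such a study". That estimate should come from one stated model.

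**Working it through.** **Inputs.** From section 9.0: SD of change 3, difference 1.7, two-sided 5%. From section 4.1: 40 participants, taken as 20 per arm. From section 8.3: ten covariates. Sex is stratified, which leaves nine not balanced by design. Assumed, because the plan is silent: that these nine are the candidates, that each is tested at 5%, and that flagged ones enter mechanically.

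**1. The plan's own power figure.** At 50 per arm, SE = 3 × √(2/50) = 0.600 and 1.7/0.600 = 2.83. The noncentral t with 98 df gives 80.1%, which reproduces the stated 80% for an unadjusted comparison. At 20 per arm, SE = 3 × √(2/20) = 0.949 and 1.7/0.949 = 1.79. With 38 df, power is 41.6%, the reference for what follows. (That the power statement uses 100 participants is a separate matter.)

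**2. How often the trigger fires by chance.** For nine independent covariates the probability is 1 − (1 − a)^9:

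| Test level a (assumed) | Chance of switching |
|---|---|
| 5% | 1 − 0.95^9 = 37% |
| 10% | 1 − 0.90^9 = 61% |
| 20% | 1 − 0.80^9 = 87% |

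The missing cut-off alone moves the outcome from usually ANOVA to nearly always ANCOVA. If the covariates are correlated, the 5% figure falls to 32-34% at a pairwise correlation of 0.3 and to 27% at 0.5.

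**3. What a switch does.** The rule was simulated at 20 per arm with SD 3, nine independent covariates unrelated to outcome and 5% t-tests, adding the flagged covariates to the model.

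| | True difference 0 | True difference 1.7 |
|---|---|---|
| Model switches | 37-38% | 36-38% |
| p<0.05 verdict changes, of switched trials | 3-4% | 13-15% |
| p<0.05 verdict changes, of all trials | about 1% | about 5% |
| Rejection rate, rule | 5.0% | 39-40% |
| Rejection rate, plain ANOVA | 5.0% | 41-42% |

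In switched trials the estimate moves by a median of about 0.27 points, or 0.27/0.949 = 0.28 of its standard error. If baseline K-L is added to the candidates, the switch rate is 39-42% and the verdict changes in 6-7% of all trials at 1.7. If one of ten covariates is correlated 0.3, 0.5 or 0.7 with change, the rule's type I error is 4.9%, 4.2% or 3.9%, so it becomes conservative.

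**4. What a fixed model would give.** With equal variances at baseline and follow-up and correlation ρ between them, adjusting for baseline multiplies the variance of the treatment estimate by (1 + ρ)/2 relative to raw change: 0.85 at ρ = 0.7 and 0.95 at ρ = 0.9. Simulated power at a difference of 1.7, with treatment, baseline and sex in the model:

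| ρ (assumed) | Raw change | Fixed ANCOVA |
|---|---|---|
| 0.7 | 41.3% | 46.1% |
| 0.8 | 41.9% | 44.3% |
| 0.9 | 41.2% | 42.3% |
| 0.95 | 41.4% | 41.0% |

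A second run put the gain at ρ = 0.7 at about 3 points, hence the range of 3-5. The documents give no value of ρ.

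**The case against.** The strongest reply has four parts.

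- **This is a pilot.** The plan calls itself exploratory, declines multiplicity adjustment and leaves adequate power to a later trial. Counting crossings of p = 0.05 at a difference where power is about 42% shows the rule at its most sensitive. This stands, and it is why the weight is minor. It does not remove the need for a stated model, since the pilot's effect sizes are meant for reuse.
- **The simulated rule is a construction.** The plan does not say that the section 8.3 items are the candidates or that 5% tests decide, and several items are not naturally continuous. This also stands: 37% illustrates one reading and is not a property of the plan. But the rule can only be simulated on assumptions because it is undefined.
- **Masking limits steering.** Section 6.3 says: "Only when all primary data analyses are completed will our OT reveal which group is treatment" A, and section 10.7.a has the therapist alone hold the "designation until the study data set is closed and all analyses are finalized". Radiographs are read in a batch after the study (section 8.4.i), while baseline tables are reported during it (section 10.10.a), so imbalance in clinical covariates can be seen before any K-L score exists. This narrows the room for outcome-driven choice. It does not fix the model: the size of the A-B difference is visible without knowing which group is traction, and the baseline K-L sum is itself read late.
- **The gain is small.** True: it is a few points at best and may be nil.

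A reader might infer that the rule inflates type I error. Applied mechanically, it does not. Error of about 9-11% arises only if covariates are chosen freely after the results are seen, and nothing in the documents indicates that. Nor is the default estimate biased: unadjusted change is unbiased under randomisation.

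A reader might also extend the point to Aim 3, where the plan will "compare mean change of each symptom and function outcome during follow-up between traction therapy and the control groups with linear regression model" for repeated measures. That wording fits either raw change or a baseline-adjusted comparison. It is an ambiguity, not a shown fault.

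**Conclusion.** The point holds for Aim 4 and is minor. The primary structure analysis depends on an undefined trigger that, under randomisation, responds only to chance, and the trigger buys nothing over plain ANOVA in the setting examined. The sizes (a switch in about 37% of trials; a changed verdict in about 5% of all trials at a difference of 1.7 and about 1% at no difference) rest on 20 per arm, the plan's SD of 3, nine independent covariates unrelated to outcome and an assumed 5% test level. The documents do not support a claim of bias, of inflated type I error, or of a large loss of power.

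**What to change.** In section 9.0, Specific aim 4, delete the imbalance-triggered sentence. For each radiographic sum, pre-specify an ANCOVA with treatment, the baseline value of that sum, and sex as the randomisation stratum. Keep any other covariates, named in advance, for sensitivity analysis only. Baseline comparisons can remain as description.

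The cost is a change of wording and two model degrees of freedom; the baseline radiographs and sex are already collected. One sentence on how the baseline value enters the Aim 3 repeated-measures model could be added at the same time, as a clarification.

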## 10.0 Supporting Documentation and Operational Considerations

### 10.1 Protocol Deviations

A protocol deviation is any noncompliance with the clinical trial protocol, International Conference on Harmonization Good Clinical Practice (ICH GCP), or Manual of Procedures (MOOP) requirements. The noncompliance may be either on the part of the participant, the investigator, or the study site staff. As a result of deviations, corrective actions are to be developed by the site and implemented promptly.

It is the responsibility of the site investigator to use continuous vigilance to identify and report deviations within 2 working days of identification of the protocol deviation. All deviations must be addressed in study source documents, reported to the NIAMS Program Official and their executive secretary, KAI. Protocol deviations must be sent to the BCM Institutional Review Board (IRB) within 5 business days of becoming aware of the event only if there is a compliance concern. The site investigator is responsible for knowing and adhering to the reviewing IRB requirements. Further details about the handling of protocol deviations will be included in the MOOP.

An example of a protocol deviation will include if the participant attends the in-person clinic visit outside of the visit window or a missed in person clinic visit.

### 10.2 Study Discontinuation and Closure

This study may be temporarily suspended or prematurely terminated if there is sufficient reasonable cause. Written notification, documenting the reason for study suspension or termination, will be provided by the suspending or terminating party to the PI. The PI will promptly inform study participants, the BCM IRB, the NIAMS and KAI of the

suspension or termination and provide the reason(s) for such action. Study participants will be contacted, as applicable, and be informed of changes to study visit schedule.

Circumstances that may warrant termination or suspension include, but are not limited to:

- Determination of unexpected, significant, or unacceptable risk to participants
- Demonstration of efficacy that would warrant stopping
- Insufficient compliance to protocol requirements
- Data that are not sufficiently complete and/or evaluable
- Determination that the primary endpoint has been met
- Determination of futility

Study may resume once concerns about safety, protocol compliance, and data quality are addressed, and satisfy the NIAMS, BCM IRB and/or Food and Drug Administration (FDA).

*If the study is prematurely terminated, refer to Section 7.2, **Study Intervention Discontinuation**, for handling of enrolled study participants.*

**10.3 Data Archiving / Quality Control / Quality Assurance.** All study data will be collected and managed using the REDCap electronic data capture tools, designed to comply with HIPAA regulations. This is a VA approved electronic data capture software. It is designed to support data capture for research studies from anywhere in the world with secure web authentication, data logging, and Secure Sockets Layer (SSL) encryption. It provides: 1) an intuitive *interface for validated data entry* 2) *audit trails* for tracking data manipulation and export procedures 3) *automated export procedures* for seamless data downloads to common statistical packages, an essential feature for data back-up and 4) user-friendly procedures for importing data from external sources. We will store all consent forms, all participant questionnaires, and study information on REDCap. On a weekly basis, all acquired information will be uploaded to a VA server on the VA network, protected by user login and passwords and we will run simple logic checks to assure the data is downloading appropriately. All servers are backed up daily to ensure data protection. Weekly full backups are stored in a vault at a secure remote location. The heart of the server system is a Hewlett Packard Itanium System running under the UNIX operating system. This server is used for managing and analyzing the large datasets. The Itanium server has four 1.5-gigahertz (GHz) Itanium central processing units (CPUs) that have instruction set architecture of 64 bit Intel microprocessors (IA64), 28.0 gigabyte (GB) of random access memory (RAM), and approximately 8 terabytes (TB) of disk storage. In addition to the Hewlett-Packard Itanium, six Dell servers run the Windows operating system, used for network applications, Structured Query Language (SQL) database, file sharing, and print sharing with a total storage capacity of 4TB.

#### **10.4 Publication and Data Sharing Policy.**

National Institutes of Health (NIH) Public Access Policy, which ensures that the public has access to the published results of NIH funded research. It requires scientists to submit final peer-reviewed journal manuscripts that arise from NIH funds to the digital archive [PubMed Central](#) upon acceptance for publication.

This study will comply with the NIH Data Sharing Policy and Policy on the Dissemination of NIH-Funded Clinical Trial Information and the Clinical Trials Registration and Results Information Submission rule. As such, this trial will be registered at ClinicalTrials.gov, and results information from this trial will be submitted to ClinicalTrials.gov. In addition,

